## 4.8.7. **Concomitant Medications**

Concomitant medications will be coded using the WHO Drug dictionary. Frequencies and percentages will be presented for each treatment group and overall by the first level anatomical main (ATC 1) group and preferred name.

All medications administered between the date of the Month 6 visit and the date of the last dose of extension study drug, inclusive, (i.e., all medications starting or ongoing during the time interval) are concomitant to the extension treatment period.

Concomitant medications tables will be presented for the following periods: Month 6 to Month 12 (Extension treatment period) and Month 12 to Month 6 ExFU (Extension follow-up period) as defined in section 4.2.12.

Sponsor:	ObsEva			
Protocol:	19-OBE2109-005			
Document Version No.:	1.0	Document Date:	18-MAY-2021	

The use of prior and concomitant medications will be included in a by-subject data listing.

## 4.8.8. Transvaginal Ultrasound (TVUS)

TVUS was to be performed at Month 6, Month 9, Month 12, as well as Month 3 and Month 6 of Extension Follow-up period.

The actual value, change from baseline and change from baseline 2 (only for subjects in the placebo arm in the main study) will be summarized by treatment group for uterus length, width, and depth in mm and corresponding uterine volume in cm3, endometrium thickness in mm.

The number and percentage of subjects with ovarian endometrioma with a diameter of 7 cm or greater, and development of any uterus, left ovary or right ovary abnormality over time will be presented by treatment group.

All TVUS data for each subject will be provided in data listings.

## 4.8.9. **Other Examinations**

#### 4.8.9.1. Endometrial biopsy

Biopsies for histological assessment were obtained for each subject at the following timepoints:

- Month 6 or one at Month 12 if endometrium thickness via TVUS is > 5 mm
- Month 1 ExtFU, 3 ExtFU, or 6 ExtFU if not obtained at Month 12 or if the preceding biopsy diagnosis is different than "benign endometrium"

On biopsies with a primary diagnostic 1 either "hyperplasia" or "Malignant Endometrial Neoplasm", a second read should be done at other visit than screening. For hyperplasia diagnostic, in case of multiple readings of the same sample, the most severe diagnostics will be selected for the statistical analysis, considering the following order, from less severe to more severe: simple without atypia hyperplasia < simple with atypia hyperplasia < complex without atypia hyperplasia. For Malignant Endometrial Neoplasm, we assume that there will be no difference on diagnostic between the readings.

Biopsies with a primary diagnostic 1 "Benign Endometrium" will be analyzed in the classification "Benign Endometrium without Hyperplasia or Atypia".

A summary at each time point will be performed (number and percentage of subjects with normal, abnormal, not assessable).

Sponsor:	ObsEva			
Protocol:	19-OBE2109-005			
Document Version No.:	1.0	Document Date:	18-MAY-2021	

Biopsy assessment will be summarized by classification (primary diagnosis 1) and primary diagnoses (diagnoses 2, 3 and 4) at each visit. Subjects will be counted only once for classification (primary diagnosis 1) and a subject could be in several diagnoses (e.g. if for example diagnoses 2 and 3 are fulfilled).

Possible results by classification (primary diagnosis 1) and primary diagnoses (diagnoses 2, 3 and 4) are:

- Benign Endometrium without Hyperplasia or Atypia: Proliferative, Atrophic, Metaplastic Changes, Secretory, Indeterminate, Inactive, Polyp, Endometritis, Menstrual phase, Other
- Hyperplasia: Simple with Atypia, Simple without Atypia, Complex with Atypia, Complex without Atypia

Malignant Endometrial Neoplasm: Carcinoma, Sarcoma, Other Malignant.

Endometrial biopsy results, including multiple readings, will be reported in listings.

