Overall, there were no clinically meaningful changes from baseline in laboratory parameters, vital signs, physical examination, or lipid measurements including HDL cholesterol, LDL cholesterol, and triglycerides in any group.

Gynecological examinations showed a small number of abnormal clinically significant results, but with a higher frequency noted for uterus and ovaries. At Week 24, reductions from baseline in endometrial thickness and uterus volume were more notable at the higher doses of linzagolix (100 mg and 200 mg) compared to the lower doses. This pattern was not observed at Week 52. Endometrial biopsy did not raise any safety concern.

Overalll, the safety findings at the end of 52 weeks of treatment revealed no new safety issues. Patterns of BMD loss were similar to the main study.

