10.2.1.5 Study visit: Month 12 (Day 337 ± 3 days)

The following tests and evaluations will be performed :

- eDiary completion compliance check

- ePRO and ClinRO completion, ideally before any other procedures or assessments: EHP-30, EQ-5D-5L, PROMIS, mPGIS, PGIC, HRUQ, HRPQ, SSIQ andd PSIQ (mPGIS and PGIC must be completed last)
- Concomitant treatments recording
- AE recording
- Completion of the paper C-SSRS questionnaire (version for "already enrolled subjects" (see Appendix R) for patients responding to the C-SSRS for the first time during the study, or version "since last study visit" (see Appendix S) for patients for whom the C-SSRS was completed at the previous study visit)
- Final IMP accountability based on blisters
- ECG (at about the same time as but before the PK sample)
- Physical examination, including weight recording
- Vital signs (BP and heart rate)
- Urine pregnancy test
- Gynecological examination
- Manual breast examination (by palpation)
- TVUS of uterus
- Urinary protein dipstick
- Fasting (overnight) blood samples for haematology, coagulation parameters, chemistry, lipids, hormones (E2, LH, P4 and SHBG) and bone biomarkers
- PK sample (the time of dose administration on previous 4 days and time of PK sampling will be recorded)
- Endometrial biopsy, unless the endometrium thickness in TVUS is ≤ 5 mm, in which case no endometrial biopsy will be necessary (see section 10.4.5). Appropriate photo documentation of the endometrium thickness is mandatory.
- BMD assessed by DXA for femoral neck, hip and spine. DXA can be performed up to 10 days prior to the study visit which allows to get the DXA results ideally at the time of the Month 12 study visit at the latest.
- The subject will be verbally asked which treatment she believed she received during the Treatment Period in the extension study. The answer will be recorded in the eCRF.
- Contraception dispensing (if applicable) and counselling
- Prescribe/dispense permitted analgesics as rescue medication
- Dispense calcium and vitamin D supplementation

An additional question will be asked to the subject about the burden of filling in the eDiary (0 =not at all a burden, 10 = very much a burden). The answer will be recorded in the eCRF.

The Month 12 study visit constitutes the end of the Treatment Period pertaining to this extension study.

The subject will continue in the post-treatment 6-month Follow-Up (FU) Period.

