10.2.2.1 Study visit: Month 1 Extension FU (Month 1 ExFU)

Month 1 ExFU visit should be scheduled on Day 365 ± 7 days after main study Day 1 (or 28 days ± 7 days after last IMP intake for early discontinued subjects).

The following tests and evaluations will be performed at Month 1 ExFU visit:

- eDiary completion compliance check
- ePRO completion, ideally before any other procedures or assessments: mPGIS and PPGIC (must be completed last)
- Concomitant treatments recording
- AE recording
- Completion of the paper C-SSRS questionnaire (version for "already enrolled subjects" (see Appendix R) for patients responding to the C-SSRS for the first time during the study, or version "since last study visit" (see Appendix S) for patients for whom the C-SSRS was completed at the previous study visit)
- ECG
- Vital signs (BP and heart rate)
- Urine pregnancy test and contraception dispensing and counselling
- Urinary protein dipstick
- Blood samples for haematology, coagulation parameters, chemistry, hormones (E2, LH and P4)
- Endometrial biopsy only if diagnosis at Month 12 was different than "benign endometrium" or if no endometrial biopsy was done at Month 12 (see section 10.4.5).
- Prescribe/dispense permitted analgesics as rescue medication
- Dispense calcium and vitamin D supplementation

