10.4.5 Endometrial biopsies

At the end of the Treatment Period (i.e. at Month 12 visit), endometrial biopsy for histological assessment will have to be obtained for each subject unless the endometrium thickness in TVUS is ≤ 5 mm, in which case no endometrium biopsy will be necessary (

Figure 3).

[figure not shown]

Figure 3 : Biopsy process for Month 12 visit

During the Follow-Up Period, the schedule for endometrial biospy is as described in

[figure not shown]

Figure 4 below.

[figure not shown]

Figure 4 : Biopsy process for the Follow-Up Period visits

The endometrial biopsies will be analyzed by a central laboratory blinded to treatment group. Endometrial biopsies of hyperplasia of any type will be submitted for assessment by three independent expert pathologists who are blinded to the treatment and to one another's assessment.

At any time during the study, in case of endometrial biopsy diagnosis being hyperplasia of any type (with or without atypia) or worse (neoplasm) for patient on treatment, the laboratory will send an alert to the site and the Sponsor. The medical monitor will contact the sites to discuss the proceeding in line with local practice. The subject will be discontinued from the treatment, will enter the follow-up period and will be advised to consult for gynecological evaluation and treatment.

Biopsy should be recommended (for cause) for subjects with heavy/suspicious bleeding. Results from these procedures should be documented in the eCRF.

Endometrial biopsy samples will be performed with the Pipelle de Cornier® (or equivalent), as described in the manual provided by the central laboratory.

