#### 2.5.3. Safety Variables

Safety endpoints include:

- Change from baseline to each scheduled assessment in BMD measured by DXA of lumbar spine (L1-L4), femoral neck, and total hip
- Incidence and severity of treatment emergent adverse events (TEAEs)
- Incidence and severity of hypoestrogenic TEAEs (hot flush)
- Changes in clinical laboratory assessments (hematology, biochemistry, coagulation parameters, hormones, lipids and urinalysis) from baseline to each scheduled assessment
- Any pathological changes from baseline in the endometrium as assessed by histology from endometrial biopsies
- Changes from baseline to each scheduled assessment in any other safety parameter including weight, vital signs, ECG, gynecological assessments and endometrial thickness

Safety analyses are described in Section 4.8.

Note that the endpoint "Time to the first post-treatment menses" was initially planned in the protocol, but will not be described in this SAP, because the study was stopped prematurely and all subjects couldn't be followed to evaluate this endpoint.

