- Table 14.4.5.8 Lipids Parameters Shifts from Baseline Based on Clinical Findings from Month 7 up to Month 6 Extension Follow-up – Extension Safety Analysis Set
- Table 14.4.5.9 Lipids Parameters Shifts from Baseline 2\* based on Clinical Findings from Month 7 up to Month 6 Extension Follow-up – Extension Safety Analysis Set – subset of subjects who are in the placebo arm (actual arm) in the main study
- Table 14.4.5.10 Lipids Parameters Shifts from Baseline Based on Normal Ranges from Month 7 up to Month 6 Extension Follow-up – Extension Safety Analysis Set
- Table 14.4.5.11 Lipids Parameters Shifts from Baseline 2\* based on Clinical Findings from Month 7 up to Month 6 Extension Follow-up – Extension Safety Analysis Set – subset of subjects who are in the placebo arm (actual arm) in the main study
- Table 14.4.6.1 Serum levels of P4, SHGB and LH from Month 7 up to Month 6 Extension Follow-up – Extension Safety Analysis Set
- Table 14.4.6.3 Proportions of Subjects with P4 at Least once >10.0 nMol/L from Month 6 to Month 12 Extension Safety Analysis Set
- Table 14.4.7.1 Vital Signs by Visit from Month 7 up to Month 6 Extension Follow-up Extension Safety Analysis Set
- Table 14.4.8.1 Physical Examination Findings from Month 9 up to Month 6 Extension Followup – Extension Safety Analysis Set
- Table 14.4.8.2 Physical Examination Findings Shifts from Baseline from Month 9 up to Month 6 Extension Follow-up – Extension Safety Analysis Set

Sponsor:	ObsEva		
Protocol:	19-OBE2109-00	5	
Document Version No.:	1.0	Document Date:	18-MAY-2021

- Table 14.4.8.3 Physical Examination Findings Shifts from Baseline 2\* from Month 9 up to Month 6 Extension Follow-up – Extension Safety Analysis Set – subset of subjects who are in the placebo arm (actual arm) in the main study
- Table 14.4.9.1 ECG QTcF by Visit from Month 7 up to Month 6 Extension Follow-up Extension Safety Analysis Set
- Table 14.4.9.2 ECG Findings from Month 7 up to Month 6 Extension Follow-up Extension Safety Analysis Set
- Table 14.4.10.1 Gynecological Examination Findings by Visit from Month 9 up to Month 6 Extension Follow-up – Extension Safety Analysis Set
- Table 14.4.11.2 Breast Examination Findings by Visit from Month 9 up to Month 6 Extension Follow-up Extension Safety Analysis Set
- Table 14.4.12.1 Endometrial Biopsy Findings by visit from Month 12 up to Month 6 Extension Follow-up – Extension Safety Analysis Set

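### Biopsy results are tabulated only by visit, each visit samples a different selected subset, and no planned row gives the proportion of treated women with endometrial pathology

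*SAP*

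**What the plan says.** The safety endpoint in SAP 2.5.3 (also Protocol 7.2) is "Any pathological changes from baseline in the endometrium as assessed by histology from endometrial biopsies". Endometrial health is a named safety objective (Protocol 6.2, SAP 1.2).

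Sampling is conditional:

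- **Month 12.** Protocol 10.2.1.5 requires a biopsy "unless the endometrium thickness in TVUS is ≤ 5 mm, in which case no endometrial biopsy will be necessary". Protocol 10.4.5 repeats the rule, and SAP 4.8.9.1 gives the time point as "Month 6 or one at Month 12 if endometrium thickness via TVUS is > 5 mm".
- **Month 1 follow-up.** Protocol 10.2.2.1 calls for a biopsy if the Month 12 diagnosis was other than benign, "or if no endometrial biopsy was done at Month 12". Month 3 follow-up works the same way (Protocol 10.2.2.2).
- **Month 6 follow-up.** Protocol 10.2.2.3 ties the biopsy only to there being none at Month 12 or later. Protocol Appendix B footnote 2 and SAP 4.8.9.1 also include a preceding non-benign result.
- **Any time.** For-cause biopsies are recommended for heavy or suspicious bleeding (Protocol 10.4.5). Women who withdraw during treatment have the Month 12 procedures at withdrawal (Protocol 10.7.2, SAP 4.2.7).

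The planned output is by visit: "A summary at each time point will be performed (number and percentage of subjects with normal, abnormal, not assessable", followed by classification and diagnosis at each visit. Table 14.4.12.1 is "Endometrial Biopsy Findings by visit from Month 12 up to Month 6" Extension Follow-up, and Table 14.4.12.2 covers the same span. Results are also listed by subject (Listing 16.2.9.11). The biopsy denominator is not stated. The general rule in SAP 4.2.1 points to non-missing values, while both tables are titled on the Extension Safety Analysis Set.

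**The concern.** A percentage by visit is easy to interpret when the same women are assessed at each visit. Here membership of a row depends on endometrial thickness and on earlier results. The Month 12 row leaves out everyone at or below 5 mm. The follow-up rows combine two unlike groups: women sampled for the first time off drug, and women re-sampled because something was found. A benign Month 12 result takes a woman out of all later rows, whereas a persistent abnormal one keeps her in. The rows cannot be added, and none answers how many treated women had endometrial pathology.

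The SAP uses per-woman or change-from-baseline summaries elsewhere: shifts for laboratory data (4.8.4) and physical examination (4.8.5), an at-least-once proportion for progesterone (4.8.4), and an any-time summary for the C-SSRS (4.8.10). Biopsy has none of these, although its endpoint is worded as any change from baseline and baseline biopsy results are summarised (4.5.2). At stake is whether the report can give an interpretable figure for a named safety objective.

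**Working it through.** The plan gives no figure to reproduce here. There are two checks: which biopsies can reach a table row, and what the rows would show under stated assumptions.

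**1. Biopsies that reach no row.** SAP 4.2.10 uses early-discontinuation data only if they fall within ±14 days of a visit at which that assessment is planned. Unscheduled assessments follow the same window. In the treatment period, biopsy is planned only at Month 6 (Day 169) and Month 12 (Day 337) (SAP Tables 1 and 3).

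- Month 6 window ends: 169 + 14 = Day 183.
- Month 12 window starts: 337 − 14 = Day 323.
- Gap: Days 184 to 322, that is 322 − 184 + 1 = 139 days.
- Treatment days: Day 169 to Day 336, that is 336 − 169 + 1 = 168 days; 139/168 = 83%.

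An on-treatment withdrawal or for-cause biopsy in that gap is assigned to neither visit. One assigned to Month 6 is not shown either, because both tables start at Month 12. Take a woman who withdraws on Day 250, treating her withdrawal visit as her Month 12 visit. If the biopsy is benign she is not re-sampled and appears nowhere. If it is non-benign she is re-sampled about 28 days later and appears only with the off-drug result.

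**2. Off-drug samples.** Month 1 follow-up is about 28 days after the last dose, that is 28 × 24 = 672 hours. With the half-life of about 15 to 20 hours in Protocol 5.5.1, 672/20 ≈ 34 half-lives. A first biopsy at that visit is not on-treatment histology.

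**3. What the rows would show, per 100 treated women.** These inputs are assumptions, since the documents give none of them: 20% to 80% of women above 5 mm at Month 12; 50% to 100% of non-benign results persisting; every woman unbiopsied at Month 12 sampled at Month 1 follow-up. Let T be women above 5 mm, a the non-benign among them, U = 100 − T, b the non-benign among U, and p the persistence.

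- Month 12 row = a/T
- Month 1 follow-up row = (b + p·a)/(U + a)
- Month 3 follow-up row = p, since only previously non-benign women remain
- Ever non-benign = (a + b)/100

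Worked case, 2% at any thickness, T = 50, p = 1: a = 1 and b = 1. Month 12 = 1/50 = 2.0%; Month 1 = (1 + 1)/(50 + 1) = 3.9%; Month 3 = 100%; ever = 2.0%.

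| Assumed non-benign rate | Month 12 | Month 1 follow-up | Month 3 follow-up | Ever |
|---|---|---|---|---|
| 2% at any thickness | 2.0% | 2.2% to 9.3% | 50% to 100% | 2.0% |
| 3% above 5 mm, 0.5% at or below | 3.0% | 0.9% to 11.2% | 50% to 100% | 1.0% to 2.5% |

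**4. The unstated denominator.** If all treated women are used instead, the Month 12 row in the 2% case is 0.4% (T = 20) to 1.6% (T = 80). Unbiopsied women are then counted as free of pathology, so the row is only a lower bound. Neither denominator yields the per-woman proportion.

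**The case against.** A reader might infer two stronger things, and the documents support neither.

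- **That the Month 12 row overstates pathology.** This happens only if pathology concentrates above 5 mm. At equal rates the row is unbiased among biopsied women (2.0% against 2.0% above). The documents do not say which case applies.
- **That selection differs between regimens and distorts their comparison.** Protocol 5.5.3 reports that at Week 24 "reductions from baseline in endometrial thickness and uterus volume were more notable at the higher doses of linzagolix", but then says the pattern was not seen at Week 52, the Phase 2b time point nearest Month 12. The 200 mg arm of that study was also reduced to 100 mg after Week 24, and its results are cited as showing the need for add-back therapy. It is a poor guide to 200 mg with add-back therapy at Month 12.

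The main defence is that other outputs fill the gap. Every biopsy is listed. Hyperplasia or worse on treatment leads to discontinuation, and an abnormality that does so is reportable as an adverse event (Protocol 12.1.2). Adverse events are counted once per woman, in a window that runs 30 days past treatment (SAP 4.8.2). Women with hyperplasia in the main study were not eligible (SAP 2.3.1), so a later hyperplasia is nearly always new. The study is small, terminated and purely descriptive.

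Part of this stands. The listing allows derivation by hand, and for hyperplasia a baseline shift adds little. But a listing is not a summary. The adverse-event route depends on investigator reporting and shows neither who was sampled nor who was not. The SAP also places polyp and endometritis under the benign heading, so change from baseline is not only a matter of hyperplasia. Small numbers make it more important that a recurring case is not read as several.

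**Conclusion.** The concern holds as a gap in the planned summaries. The biopsy tables describe a different selected subset at each visit, count persistent cases repeatedly across rows, and omit on-treatment withdrawal and for-cause biopsies between Days 184 and 322. No planned row gives the proportion of treated women with endometrial pathology.

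The sampling rules and the 139-day gap come from the documents. Enrichment of the later follow-up rows follows from the re-biopsy rule itself. The percentages are illustrations: the share of women above 5 mm, the pathology rate and its persistence are all assumed. Actual enrolment is not stated beyond being well below target (SAP 1.2). The documents establish neither a direction of bias at Month 12 nor a difference between regimens.

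**What to change.** Add one per-woman table on the Extension Safety Analysis Set:

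- Worst diagnosis from any biopsy after the first extension dose through Month 6 follow-up, including withdrawal, unscheduled and for-cause biopsies regardless of visit window.
- Shown against the main-study baseline diagnosis, and against Baseline 2 for women who switched from placebo.
- Split by sampled on treatment and sampled off drug. The Month 12 sample, taken the day after the last dose, counts as on treatment; state how a withdrawal sample is classed.
- Numbers treated, sampled and never sampled in each group.

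The severity order in SAP 4.8.9.1 stops at complex hyperplasia without atypia, so it needs extending to cover every listed diagnosis. Keep the by-visit tables and state the number biopsied as their denominator. Reconcile Protocol 10.2.2.3 with Protocol Appendix B footnote 2 and SAP 4.8.9.1 on who is biopsied at Month 6 follow-up, because this decides who is in that row.

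The cost is one table from data already collected. Its drawback is that it puts on-drug and off-drug samples together, which the split makes visible.

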### 4.8.9.2. Gynecological and Breast examination

Gynecological Examination was to be assessed at Month 6, Month 9 and Month 12, as well as Month 3 of the extension Follow-Up period.

Breast examination (by palpation) was to be performed at Month 6 and Month 12, as well as Month 3 of the extension Follow-Up period.

A summary at each time point will be performed (number and percentage of subjects with normal, abnormal significant) for Gynecological and Breast Examinations.

Results will also be reported in listings.

## 4.8.10. Columbia-Suicide Severity Rating Scale (C-SSRS)

The C-SSRS questionnaire prospectively assess the occurrence of treatment-emergent suicidal ideation and behavior.

Subjects completed:

- either the "Baseline" C-SSRS version, capturing lifetime history of suicidal ideation and behavior, for subjects who were still in screening period in the main study,

- or the "already enrolled subjects" C-SSRS version, for subjects already enrolled in the Extension study, and who were providing answers to the C-SSRS for the first time during the study

- the "since last study visit" C-SSRS version, dedicated to subjects for whom the C-SSRS was completed at the previous study visit, for use at all remaining study visits.

The "Baseline" C-SSRS version was to be completed during Screening, or at Day 1 if not done during Screening.

CRS-BS-TP-000005 V 1.0

